## 7.4. Sample Size

Please see section 2.4.1. Sample size, justification and calculations

## 7.5. Statistical Analysis

Our aim is to evaluate the impact of thoracic Prehab with IMT compared to standard Prehab in reducing post operative pulmonary complications following surgical resection in lung cancer patients in a RCT. Statistical analysis will be performed using SPSS statistical software, version 20.0 (IBM Corporation, Armonk, NY, USA). Two-sided significance tests will be used ( $\alpha \leq 0.05$ ). Data will be presented as mean and standard deviation (SD), or median and interquartile range (IQR) for variables with a skewed distribution. Differences between groups in categorical variables will be tested with Chi square or Fisher's exact test.

For continuous data the student's t test or the Mann-Whitney U test will be used. The Wilcoxon signed rank test will be used to compare MIP and QoL at T0 and T1 and T2.

Relative risk will be calculated for post operative pulmonary complications (PPCs) graded 1-V using the Clavin Dindo classification and impact of IMT on the study group compared to the control group. Assuming a 36.7incidence of PPC after surgery in the control arm and using a significance level of 0.05 and a power of 80%, 50 patients are required in each arm."

## **8. Data Management**

### **8.1. Data collection**

Outcome measures will be collected by the principal investigator and research team onto paper initially, forming part of the physiotherapy notes. These physiotherapy notes will be kept in a locked cabinet within a secure room, which only the PI and research team will have access to.

### **8.2. Data Systems**

Outcome measures collected on paper, will be inputted into a password secure excel database, on a security- protected computer.

### **8.3. Data integrity**

The Good Clinical Research Practice (GCP) guidelines will be followed with regards to maintaining data accuracy and consistency, from data generation, to recording and destruction, including any intervening.

### **8.4. Data monitoring**

Data will be monitored electronically by the whole of the research team and escalated to the CI accordingly.

The data will be reviewed by the CI and PI in a monthly meeting.

### **8.5. Data archiving and destruction**

During the course of research, all records are the responsibility of the CI and will be kept in secure conditions. When the research trial is completed all records will be kept for 5 years, as per requirement of the Research Governance Framework and Health Board Policy that the records are kept for a further 5 years in the Health Board archive facility.

## 9. Data Handling & Record Keeping

### 9.1. Confidentiality

The CI has responsibility to ensure that patient anonymity is protected and maintained. Information with regards to study patients will be kept confidential and managed in accordance with the Data Protection Act, NHS Caldicott Guardian, Research Governance Framework for Health & Social Care 2017 and Research Ethics Committee Approval.

All PIS's will be compliant with the General Data Protection Regulation (2018) (GDPR), ensuring, appropriate transparency of data. All of the study essential documents electronic, and hard copies, will be archived for 5 years, The R&D department will make provisions for archiving and destruction of these documents.

The legal basis for processing and storing/sharing data will be Article 9.2 (j) – pseudo-anonymised (scientific research).

No patient identifiable information will be collected from subjects.

All study participants will be allocated a unique study code and no identifiable data will be captured on the data management system.

As part of the trial, direct, anonymised quotations from participants will be collected. These will be disseminated and published as part of the results of the study. For example, how subjects managed with the device, patient reported experience measures and outcome measures.

### 9.2. Study Documents

- A signed protocol and any subsequent amendments

- Current Summary of Product Characteristics/ Investigator's Brochure
- Sponsor Self-Monitoring template for the trial team to complete on a regular basis as detailed by the Monitoring section
- Current/Superseded Patient Information Sheets (as applicable)
- Current/Superseded Consent Forms (as applicable)
- Indemnity documentation from sponsor
- Conditions of Sponsorship from sponsor
- Conditional/Final R&D Approval
- Signed site agreement
- Ethics submissions/approvals/correspondence
- CVs of CI and site staff
- Laboratory accreditation letter, certification and normal ranges for all laboratories to be utilised in the study
- Delegation log
- Staff training log
- Site signature log
- Patient identification log
- Screening log
- Enrolment log
- Monitoring visit log
- Protocol training log
- Correspondence relating to the trial
- Communication Plan between the CI/PI and members of the study team
- SAE reporting plan for the study

### **9.3. Case Report Form/ Data Collection Tool**

The research team will be responsible for completing the data collection tool.

### **9.4. Record Retention and Archiving**

During the course of research, all records are the responsibility of the CI and will be kept in secure conditions. When the research trial is completed all records will be kept for 5 years,

as per requirement of the Research Governance Framework and Health Board Policy that the records are kept for a further 5 years in the Health Board archive facility.

## **9.5. Compliance**

The CI will ensure that the trial is conducted in compliance with the principles of the Declaration of Helsinki (1996), and in accordance with all applicable regulatory requirements including but not limited to the Research Governance Framework, Trust and Research Office policies and procedures and any subsequent amendments.

## **9.6. Clinical Governance Issues**

### **9.6.1 Ethical Considerations**

To address issues of geographical location, deprivation, poverty, and for people who are less likely to have access to Prehab due to for example, transport costs, SBUHB Prehab provides satellite clinics closer to patients' homes, or home visits by physiotherapists for the less able. Both male and female patients have equally availed of the service and our Health Board has a robust provision of Equality and Diversity training to all staff working in the Health Board.

The study will be registered with the local NHS Research and Development Department of the Health Board under the guidance of the NHS Research Ethics Centre and commence on receiving ethical approval and conducted to the principles of NIHR Good Clinical Practice in research.

## **9.7. Quality Control and Quality Assurance**

### **9.7.1. Summary Monitoring Plan**

The Sponsor will have the overall responsibility for ensuring the trial is monitored and will have oversight of the process.

The CI will ensure that agreements are in place, the monitoring plan is followed and that the PI is compliant with all monitoring requests.

A completed risk assessment will determine the monitoring required for this study.

### **9.7.2. Audit and Inspection**

Auditing: Definition “A systematic and independent examination of trial related activities and documents to determine whether the evaluated trial related activities were conducted, and the data were recorded, analysed and accurately reported according to the protocol, sponsor's standard operating procedures (SOPs), Good Clinical Practice (GCP), and the applicable regulatory requirement(s).”

This study may be identified for audit by any method listed below:

1. A project may be identified via the risk assessment process.
2. An individual investigator or department may request an audit.
3. A project may be identified via an allegation of research misconduct or fraud or a suspected breach of regulations.
4. Projects may be selected at random. The Department of Health states that Health Boards should be auditing a minimum of 10% of all research projects.
5. Projects may be randomly selected for audit by an external organisation.

Internal audits will be conducted by the sponsor's representative

### **9.8. Non-Compliance**

Patients who do not adhere to the proposed intervention will be offered a telephone consultation, to consider behaviours and characteristics, preferences, barriers and facilitators to enable and explore compliance. This could be done with the carer if the patient wishes. If adherence remains an issue patients will be removed from the research and will be asked to return their patient diary for analysis.

A noted systematic lack of both the CI and the study staff adhering to SOPs/protocol/ICH-GCP, which leads to prolonged collection of deviations, breaches or suspected fraud.

These non-compliances may be captured from a variety of different sources including monitoring visits, CRFs, communications and updates. The sponsor will maintain a log of the non-compliances to ascertain if there are any trends developing which to be escalated. The sponsor will assess the non-compliances and action a timeframe in which they need to be dealt with. Each action will be given a different timeframe dependent on the severity. If the actions are not dealt with accordingly, the research and development Office will agree an appropriate action, including an on-site audit.

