## Data collection

QoL data using EORTC QLQ-30 questionnaire will be collected at initial assessment (T0) and on completion of Prehab (T1) as final assessment, then post-surgery at discharge (T2) and at 1 month following surgery (T3).

Subjective outcome measures data include dyspnoea score, PS, thoracoscore, frailty index (FI), LOA and objective measures include 6-minute walk distance test (6MWD) at initial assessment (T0), after every two weeks in Prehab to assess for improvement, and finally at final assessment prior to participants proceeding to surgery (T1) (14,15,30). LOA, measured using the Borg scale of perceived exertion, will be recorded as sedentary, moderately active or active and supplemented by the 6MWD. The 6MWD will be performed using a 10m corridor instead of 30m (31). A 10 metre track along a flat corridor, will be used to measure the distance walked in metres within the 6 minutes. A 10m track was used in our previously published study and proved very effective. The American Thoracic Society guidelines state a distance of 30 metres (100 foot) should be used, however this is difficult practically. It is rare to find a 30-metre corridor in a hospital that is quiet and can allow a chair to be positioned for seated rests. A 10 metre track will be better from a health and safety point of view, as well as giving patient's privacy to focus on the self-paced walk test. These above outcome measures are already standard care for all Prehab patients (14,15).

Calculating the thoracoscore for each individual for lung resection in percentage describes the mortality risk of the individual for surgery. This is already standard operating procedure (SOP) for obtaining informed consent for lung resection surgery, and will be calculated for each participant (T0 and T1) (2,32).

The maximal inspiratory pressure (MIP) for both groups will be measured using a POWERbreathe device (Figure 2) at initial assessment (T0), on completion of Prehab (T1) and at discharge (T2). Measuring MIP is not standard practice for Prehab and will be an additional and essential outcome measure. It is required to assess the progress of each individuals improvement with the Prehab. Due consideration regarding IMT contraindications in patients to avoid harm or adverse events is included in our inclusion/exclusion criteria.

Following surgery, data on PPC's and HLOS will be collected by the researcher. This is standard practice for the prehab service.

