**Post-discharge assessment:** Our primary objective is to determine whether IMT prior to surgery with Prehab helps reduce PPC following surgery, which is up to the point of discharge from hospital (alive or dead). This is one time point. Hence, it is anticipated that all patients will complete the discharge assessment for complications. Thus, the study is not underpowered for the primary end point.

Mortality rates will be collected at discharge, 1 month, 3 months, and 365 days post-surgery.

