### 3.4. Criteria for Premature Withdrawal

Participants will be withdrawn from the study for the following reasons:

- Participants are no longer considered suitable for surgical lung resection by the MDT. Other treatment options may be considered more prudent such as radiotherapy or systematic anticancer treatment or best supportive care.
- The participant decides they no longer wish to be part of the study or have decided against surgical resection
- The research team decide it is unsafe for the participant to continue due to medical, safety and regulatory concerns. This includes adverse cardio-respiratory events relating to the patients physical conditioning as assessed by the cardiothoracic physiotherapists
- If the participant becomes lost to follow-up as deemed by the research team
- If the participant loses their capacity during the study period (including death)
- A significant increase in post-surgical mortality

Patients have the right to refuse study participation.

If a participant loses capacity to consent or withdraws consent, they will be withdrawn from the study. Identifiable data already collected with consent would be retained and used in the study. No further data would be collected or any other research procedures carried out on or in relation to the participant.

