**Cardiovascular exercises:** namely, stationary cycle ergometry and upper and lower limb resistance exercises will be performed, whilst monitoring the heart rate, blood pressure and oxygen saturations (15). The rate of perceived exertion (RPE) will be measured using the Borg breathlessness scale and used twice at every session to measure the intensity at which each patient is working and guide them to increase or decrease their effort as required.

**Home Exercise Program (HEP):** individualised home exercise programme includes daily walking plan and stair climbing exercise (15). Training enabling them to maintain activities of daily living following surgery. The HEP will be continued following discharge after surgery.

**Health education and smoking cessation advice** will be provided to all current smokers prior to surgery and support following surgery (15). Where necessary nicotine replacement therapy will be provided.

**Intervention group:** The intervention group will receive IMT in addition to a standard Prehab protocol (as above). An MIP in cmH2O, obtained at or greater than 1.5 seconds will be recorded, and the highest MIP of 3 valid breaths will be used as baseline. The IMT pressure in cmH2O will be set initially at 40% of the patients MIP. Participants will be taught to use the device in an upright position and instructed to perform six sets of six breaths with the resting times between each set of breaths reducing from 60 seconds, to 45 seconds, to 30 seconds, to 15 seconds, to 5 seconds. IMT will be used twice-daily preoperatively in the intervention group and not post operatively. Training load intensity on the IMT will be

increased preoperatively by the patient according to the rate of perceived inspiratory effort, on a modified Borg scale.

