#### **4.11. Subject Withdrawal**

Participants who withdraw/ are withdrawn from the study, will return to standard care without negative consequences. This will be made clear in initial conversations with the research team and a study withdrawal letter will be attached to the PIS, for participants wishing to withdraw at a later stage.

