#### **4.12. Data Collection and Follow up for Withdrawn Subjects**

All patients will be included in the final data analysis, by using an intention to treat analysis, thereby limiting attrition bias if patients withdraw/ are withdrawn.

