## 7.3. Safety Endpoints

Safety analysis will include rate of complications and mortality and are categorical data sets. The chi-square test or Fisher's exact test will be used to assess the safety of IMT in combination with Prehab compared with its control i.e., standard Prehab using a significance level of 0.05.

The study may be ended prematurely, if there is a significant increase in post-surgical mortality or complications in the study group.

Additionally, if any of the patients in the intervention group experience syncope symptoms whilst using the device they will be advised to stop and will be withdrawn from the study.

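### Sections 9.8 and 7.3 take patients out of the study before surgery, and no section says how the PPC outcome needed for the promised intention-to-treat analysis is then collected

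*Protocol*

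**What the plan says.** Section 4.12 places all patients in the final analysis "by using an intention to treat analysis, thereby limiting attrition bias if patients withdraw/ are withdrawn". The post-discharge paragraph of 2.4.1 treats PPC as a single assessment up to discharge and says "it is anticipated that all patients will complete the discharge assessment for complications". It infers from this that the primary endpoint is not underpowered.

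Three other sections describe exits:

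- **9.8 (non-adherence).** After a telephone consultation, "If adherence remains an issue patients will be removed from the research". The only item then requested is the patient diary. No arm is named.
- **7.3 (syncope on the device).** Of patients in the intervention group only: "they will be advised to stop and will be withdrawn from the study".
- **3.4 (capacity and consent).** "If a participant loses capacity to consent or withdraws consent, they will be withdrawn from the study". Data already held are kept, but nothing more is collected. The same section lists death in brackets under loss of capacity as a reason for withdrawal.

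On timing, 4.4 says "IMT will be used twice-daily preoperatively in the intervention group and not post operatively". On what follows, 4.11 says that withdrawn patients "will return to standard care without negative consequences". On routine recording, 2.4.1 says that after surgery "data on PPC's and HLOS will be collected by the researcher. This is standard practice for the prehab service".

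**The concern.** An intention-to-treat analysis of PPC needs the PPC outcome of everyone randomised who has surgery, whatever happened with the device. Sections 9.8 and 7.3 end study participation, not only use of the device, and they do so before the outcome can arise. If staff apply them as worded, these patients' outcomes do not enter the trial data. The analysis under 4.12 is then a comparison of those who stayed.

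That comparison is no longer protected by randomisation if removal differs between arms and is related to PPC risk. The syncope exit exists only in the IMT arm. The non-adherence exit may also fall more on that arm, because only that arm has twice-daily device training. Outcomes not collected at the time may be hard to recover later, and a rule for choosing analysis sets cannot supply them.

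**Working it through.** **1. The passages side by side**

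| Exit | Before PPC? | Is collection after exit stated? | Fits 4.12? |
|---|---|---|---|
| Non-adherence (9.8) | Yes where it concerns the device, since IMT is pre-operative (4.4) | No; diary only | Use is promised, collection is not |
| Syncope on the device (7.3) | Yes, same reason | No | Same |
| Loss of capacity (3.4) | May be before surgery, or between surgery and discharge | Yes: collection stops | No, if before discharge |
| Death (3.4) | Either | Not separately | Section 1.1 counts death as grade 5, an outcome |

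Section 4.12 has data collection in its heading but describes none.

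**2. The plan's own numbers**

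50 / (1 − 0.25) = 66.7, so 67 per arm and 134 in total. In reverse, 134 × 0.75 = 100.5, about 50 per arm. The recruitment figure reproduces, and 50 per arm is used below as the number before removal.

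**3. Illustration of the size**

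From the protocol: 36.7% PPC (2.4.1), two-sided 0.05 (2.4.2), chi-square test (7.1), 50 per arm. Assumed: no true effect; removal from the IMT arm only; a share *f* removed (10% or 20%); removed patients at *m* times the PPC risk of those who stay.

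The whole-arm rate is fixed at 36.7%, so

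rate in those who stay = 0.367 / ((1 − *f*) + *f* × *m*).

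- *f* = 0.2, *m* = 1.5: 0.367 / 1.10 = 0.334
- *f* = 0.2, *m* = 2: 0.367 / 1.20 = 0.306
- *f* = 0.1, *m* = 1.5: 0.367 / 1.05 = 0.350
- *f* = 0.1, *m* = 2: 0.367 / 1.10 = 0.334

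The rejection probability of the uncorrected Pearson chi-square was found by exact enumeration of both binomials, with controls at 0.367:

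| Removed from IMT | n (IMT v control) | *m* | Apparent relative risk | Error favouring IMT (nominal 2.5%) | Two-sided error (nominal 5%) |
|---|---|---|---|---|---|
| 20% | 40 v 50 | 1.5 | 0.334 / 0.367 = 0.91 | 5.0% | 6.1% |
| 20% | 40 v 50 | 2 | 0.306 / 0.367 = 0.83 | 8.5% | 9.0% |
| 10% | 45 v 50 | 1.5 | 0.350 / 0.367 = 0.95 | 3.7% | 5.2% |
| 10% | 45 v 50 | 2 | 0.334 / 0.367 = 0.91 | 5.2% | 6.2% |

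Checks:

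- No removal (50 v 50): 2.5% in each tail, as it should be.
- Removal unrelated to risk (*m* = 1): 2.5% favouring IMT at both 40 v 50 and 45 v 50, so no inflation.
- Equal 20% removal in both arms (40 v 40): 2.4% to 2.6% per tail, so no material inflation.
- Removed patients at lower risk (*m* = 0.5, 20% removed): 0.9% favouring IMT and 6.0% against it. The direction reverses.

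**The case against.** **The protocol already covers these patients.** Section 4.12 expressly includes withdrawn patients, so use of their data is promised. Section 2.4.1 has the researcher collect PPC and hospital stay after surgery as standard practice, with no stated limit to retained patients. This stands in part. The gap is in collection, not in intended use, and a service record should exist. But a service record does not become trial data for someone removed from the research unless the protocol says so.

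**Collection is forbidden after removal.** A reader might infer this from 3.4. The documents do not support it: the sentence ending collection covers lost capacity and withdrawn consent only. After removal under 9.8 or 7.3, collection is left unstated.

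**The bias favours IMT.** A reader might infer this from the table. It follows only if removed patients carry higher risk. The documents do not say so, and the last check shows the reverse.

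**Removal is confined to the IMT arm, or will reach 20%.** Neither is stated. Section 9.8 names no arm and comes into play only after a telephone consultation has failed. Section 3.4 allows safety withdrawals in both arms. Device syncope may be rare. The 80% adherence in 2.1 is a forecast across both arms, not a removal rate. The 9.0% case needs one fifth of the IMT arm removed, no controls removed, and a PPC risk of about 61% (2 × 0.306) in those removed.

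**The discharge-completeness statement contradicts 9.8.** This is too strong. That statement concerns assessment after surgery and is not clearly about patients removed beforehand. It shows reliance on complete PPC data, no more.

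**Keeping non-adherers costs power.** True in kind, because their inclusion dilutes the effect. The protocol text states no expected IMT-arm PPC rate, nor whether the planned effect already allows for ordinary adherence, so no power figure is given here.

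**Conclusion.** The concern holds as a conflict between stated rules. The promised intention-to-treat analysis of PPC is not secured for patients removed under 9.8 or 7.3, because nothing says their outcome is collected. For patients who lose capacity before discharge, 3.4 directly contradicts 4.12. Confidence in this textual finding is high.

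The effect on the result is unknown in size and direction. Under the illustrative assumptions, two-sided error ranges from 5.2% to 9.0%, and only the most extreme case is large. There is no inflation if removal is unrelated to risk, and none of note if it is equal across arms. Loss of capacity is not quantified, because the documents give no rate. The reason to act is that the conflict touches the primary endpoint and is cheap to remove, not that a large bias has been shown.

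**What to change.** - **9.8 and 7.3.** Separate stopping the intervention from leaving the study, and leave the device-stopping rules as they are. Suggested text: *A participant who does not adhere to the intervention, or who stops it, remains in the study in the randomised arm. Routinely recorded PPC and hospital stay up to discharge are collected for the trial unless the participant withdraws consent to data collection.*
- **3.4.** Reconcile the data rule for lost capacity with 4.12, through consent wording approved by the ethics committee that lets routine outcome data continue. State that death is an outcome (grade 5), not a withdrawal.
- **Reporting.** Give removals and their reasons by arm.

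**Cost.** A protocol amendment and possibly a consent-form amendment; the consent form was not available, so its wording must be checked. PPC and hospital stay need no new measurement, since 2.4.1 calls their collection standard practice. It does not say this of mortality after discharge, so keeping that follow-up for removed patients (to 365 days) would be extra work. Some dilution of the effect is inherent in the analysis already promised.

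**Not settled by this change.** Patients who never reach surgery have no PPC to grade (2.1 cites 75.8% ready for surgery after Prehab). How they enter the analysis needs a separate decision.
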